Homeopathic Treatment of Post-acute COVID-19 Syndrome - A Pilot Randomized Controlled Trial

NCT05104749

November 15, 2021

Homeopathic Treatment of Post-acute COVID-19 Syndrome- A Pilot Randomized Controlled Trial

Background

Post-acute COVID-19 Syndrome, or Long Covid, is being seen increasingly as a serious public health problem. While the high mortality rate and impact on the health care system of acute Covid-19 illness is profound, the long-term effects of the illness, even in those with mild disease, is just now being recognized. It is estimated that 10 to 30 percent of people diagnosed with COVID-19 experience prolonged illness beyond three weeks (Greenhalgh, Aug 2020) and roughly 1.5 percent are affected for 3 months or more (Sleat, 2020). A recent study reported that two-thirds of patients with mild to moderate COVID-19 had persistent symptoms two months after symptom onset. (Carvalho-Schneider, 2020) Considering that more than 100 million people have been infected with COVID-19 worldwide, this syndrome undoubtedly affects millions, many of them in the US.

The exact cause of Long Covid is not known but is thought by some to be due to a dysfunctional immune-inflammatory response that can affect even people who were never hospitalized. (Greenhalgh, Nov 2020). Many of the symptoms are similar to those of chronic fatigue/myalgic encephalomyelitis, including fatigue, post-exertional malaise, and brain fog. Treatment for Long Covid is mostly supportive, since there are no known conventional therapies for the syndrome at this time.

The clinical manifestations of Long Covid are varied and each patient can have a constellation of different symptoms. In an international online survey of nearly 3,800 respondents self-diagnosed with Long Covid, the most frequently reported symptoms were fatigue (98.3 percent), post-exertional malaise (89.0 percent) and cognitive dysfunction (88.0 percent). Other common symptoms included sleep difficulties (78.6 percent), emotional and mood changes (88.3 percent), headaches (77 percent), and musculo-skeletal complaints (93.9 percent). (Davis, 2020) Sixty-five percent of respondents reported symptoms persisting for more than six months.

Homeopathy was first developed in Germany by Samuel Hahnemann in the late 18th century. It is based on the principle of similars, whereby highly dilute preparations of substances that have been found to cause symptoms in healthy volunteers are used to treat patients who have similar symptoms when ill. Homeopathic medicines are prepared according to standardized methods as specified by the Homeopathic Pharmacopoeia of the United States (HPUS), which was mandated by Congress to regulate the manufacture of homeopathic medicines as part of the Food, Drug, and Cosmetics Act of 1939. Most homeopathic products are derived from plant, animal, or mineral sources and because of the highly dilute nature of the preparations, are without toxic side effects. The mechanism of action of homeopathy is not well understood, but is thought to be due to enhancement of the immune response

and other auto-regulatory systems of the body. (Bell, 2015)

Classical homeopathy, used widely by medical practitioners for acute and chronic illnesses, involves a 60-90 minute initial consultation during which a wide collection of physical, general, and mental-emotional symptoms are elicited from the patient. An individualized homeopathic medicine is prescribed, matching the specific signs and symptoms in that patient with those known to be associated with a particular medicine in the homeopathic literature. Using this individualized approach, two or more people with the same diagnosis may be given different medicines, depending on symptoms.

Previous clinical studies have shown classical homeopathy to be superior to placebo in treating a wide variety of illnesses (Mathie, 2014), including chronic diseases with symptoms similar to long COVID, such as fibromyalgia (Bell, 2004) and chronic fatigue syndrome (Weatherley-Jones, 2002). Because homeopathy is a system that treats the whole person, taking into account physical, emotional, and mental symptoms, it is likely to be of particular value to people suffering from the myriad symptoms associated with Post-acute COVID-19 Syndrome.

Hypothesis/Purpose

Our ultimate goal is to determine whether an individually prescribed homeopathic medicine has an effect greater than a placebo and is a viable treatment option to improve fatigue and quality of life for patients suffering from the symptoms of Post-acute COVID-19 Syndrome. We hope to achieve this goal by conducting a clinical trial that is scientifically rigorous and clinically relevant. Because such a trial would be costly, we first need to do a pilot study that demonstrates our ability to conduct a fullscale trial successfully. Expected results of this pilot study will be to obtain sufficient experience and preliminary feasibility data to justify a larger clinical trial of this hypothesis.

Technical Objectives

Our objectives for the study are to: 1) identify efficient means of recruiting subjects, 2) test and refine our initial study design and treatment protocol, 3) evaluate the instruments for assessing treatment outcomes, 4) estimate sample sizes that will be required in the full-scale trial, 5) determine which homeopathic medicines are most often prescribed for this syndrome, and 6) determine whether there is a measurable effect size difference or positive trend in reduction of symptoms in patients treated with homeopathy.

Methods

Overview: In this double-blind pilot study, 66 patients who have tested positive for COVID-19 and

who have had unexplained fatigue for at least 60 days, as well as at least one other symptom of Postacute COVID-19 syndrome will be randomized to one of two treatment arms: classical homeopathy or placebo. Treatment will be provided by trained homeopathic practitioners, who will see the patients at 4 week intervals over the course of 12 weeks. Fatigue scores and general health status as measured by the SF-36 will be measured at entry to the study and at 4 week intervals for 12 weeks. The MYMOP score of specific symptoms will be administered at entry to the study and at the end of 12 weeks.

Recruitment: Subjects will be recruited from advertisements on Facebook. We hope to enroll 15-20 patients per month during the 4 month enrollment period. We will use an online survey to screen potential subjects to determine eligibility. Those who are eligible will be scheduled for a telephone screening appointment, during which eligibility will be confirmed and informed consent will be obtained using a consent form approved by the Southwest College of Naturopathic Medicine Human Subjects Committee. Baseline questionnaire data will be collected, including the Fatigue Assessment scale (FAS), the SF-36 quality of life survey, and the Measure Yourself Medical Outcomes Profile (MYMOP).

Eligibility: Patients entered into the study will be ages 18-64 and have a confirmed diagnosis of COVID-19 by previous PCR testing. They will also have a history of persistent, unexplained fatigue for at least 60 days since diagnosis of COVID-19, one other symptom consistent with the syndrome, and a FAS score of 22 or above. Subjects must also have adequate cognitive function to be able to give informed consent and be technologically competent to complete online forms and perform video calls. They must also be willing to fill out regular questionnaires and to use homeopathic medications.

Exclusions: Patients taking steroids, immunosuppressives, or opioid analgesics or who have opioid or other substance dependence and/or are undergoing treatment for substance abuse will be excluded from the study. Patients who were treated in an Intensive Care Unit for Covid-19 and those with concurrent health problems such as active cancers, clinically significant kidney, heart, or hepatic impairment will be excluded. Those diagnosed prior to COVID-19 infection with chronic fatigue syndrome, fibromyalgia, Lyme disease, or chronic psychiatric or neurological illness will also be excluded. Also excluded will be women with suspected or confirmed pregnancy and those who are breastfeeding, those who are enrolled in another trial. Those who are currently being treated by a homeopathic practitioner will also be excluded as well as those who have started a new medication or treatment for Post-acute Covid-19 within the past two months.

Treatment: At the initial visit via video conferencing, a licensed homeopathic practitioner (MD, DO, ND, PA, NP) will conduct a thorough homeopathic evaluation and determine the specific homeopathic medication that seems best suited for each subject. Homeopathic practitioners will have a

minimum of five years in practice and be members of a professional homeopathic organization. Because of the individualized nature of classical homeopathic treatment, the usual paradigm of a clinical trial whereby all patients receive the same medicine cannot be followed. Instead, the method of classical homeopathic treatment as practiced in the real world will be evaluated, with one specific medicine prescribed for each patient at the initial visit. Medicines prescribed must be listed in the Homeopathic Pharmacopoeia of the United States (HPUS). The homeopathic dosage and repetition of doses will be chosen by each practitioner based on the clinical characteristics of the subject. Practitioners will be able to change the homeopathic medicine as needed during the course of the trial, in the same way they would in their usual practice.

The homeopathic prescription will be communicated to a homeopathic pharmacist, who will use a randomization scheme prepared by a third party for the patients to receive either the individualized medicine or a placebo, both of which will be identical in taste, appearance, odor, and packaging. Study medications will be express mailed to subjects' home addresses in packages that do not reveal personal information about the subject, along with dosage instructions. Existing conventional and integrative therapies that the subjects are using at the time of enrollment will be documented and subjects will be asked not to change, add, or remove any treatment unless recommended by their own conventional treating provider(s).

Randomization and blinding: Subjects in the study will be randomly assigned to receive individualized homeopathic treatment or placebo (1 : 1). After the confirmation of eligibility, subjects will be randomized with concealment. Every subject will be assigned with a number and a third party will randomize the subjects to each of the 2 study groups using computer generated random numbers. Randomization will be stratified by age (< or > 50) and duration of Long Covid symptoms (< or > 6months), in permuted blocks of four or six. Randomization will be known only to the homeopathic pharmacist, who will not break the code until after treatment of each subject is completed. An exception to this will be when a research subject suffers an unexplained severe event. In such a case, the randomization code will be broken and the subject withdrawn from the study.

Follow-up: Subjects will have follow-up visits by video with the homeopathic practitioners at 4, 8, and 12 weeks following the initial consultation. At each of these visits, the patients will be reevaluated, adverse side effects will be inquired about, and the classical homeopathic prescription will be renewed or revised, which will again be filled by the homeopathic pharmacist and mailed to the subjects. Although the specific homeopathic prescription might change, subjects randomized to each group will continue to receive placebo or active medicines throughout the study.

The subjects will also complete online questionnaires at 4, 8 and 12 weeks after the initial visit to

evaluate outcomes. At the end of the 12 week study period, those subjects who received placebo will be given the option to receive a verum homeopathic medicine and an additional follow-up visit after 6 weeks will be scheduled for them.

Outcomes:

The primary outcome measurements:

- Fatigue Assessment Score (FAS) at baseline, week 4, week 8 and week 12
- General health status, using the SF-36 at baseline, week 4, week 8 and week 12 Secondary outcome measurements:
- Measure Yourself Medical Outcomes Profile (MYMOP), in which each patient chooses the two most bothersome symptoms to record and follow (at study entry and at the end of 12 weeks)
- The number of subjects who have FAS ≤ 21 will be compared at week 4

Analysis: Because this is a pilot study with a small sample size, statistical tests are unlikely to reveal any statistically significant differences. However, the data will be summarized and analyzed as if this were a full-scale trial in an intention to treat analysis by the study statistician.

- Demographic data and baseline features will be compared using independent sample t-test and chi-square test for continuous and categorical variables respectively. (Age, sex, duration of symptoms, co-morbidities)
- Missing values will be handled by single imputation by last observation carried forward to handle missing data at the analytical stage.
- The Fatigue assessment scale (FAS) and the SF-36 (8 domains) from baseline (Day=0) and at 4-, 8-, and 12-week follow up will be analyzed by repeated-measure analysis of variance (treatment x time interaction).
- The Measure Yourself Medical Outcomes Profile (MYMOP) collected at baseline and at week 12 will be analyzed by independent sample t-test if normal or Wilcoxon ran sum test if not.
- The proportion of subjects who 'return to normal' (ie have FAS ≤21) will be compared at week 4 with chi-square test.
- Analyses will be performed using SPSS software, version 26. Two-tailed P < 0.05 will be used to denote statistical significance.
- Evidence of non-significant trends will be noted, and the variability of the FAS will be used for sample size estimation for the full-scale trial.

All modifications to this study will be approved by the Human Subjects Committee. Any adverse

event that occurs temporally related to participation in the study will be documented, whether or not it is considered to be related to the homeopathic medicines. Serious and unexpected adverse experiences will be immediately reported by telephone to the Human Subjects Committee.

References

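### Breaking the code for an unexplained severe event takes the subject out of the whole study, so later outcomes appear to be lost and are carried forward; this weakens the intention-to-treat analysis, but the likely effect is small

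*Combined protocol and SAP*

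**What the plan says.** All references are to the Methods of the combined protocol and SAP.

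- **Randomization and blinding.** The pharmacist holds the code until each subject's treatment is complete. "An exception to this will be when a research subject suffers an unexplained severe event"; in that case "the randomization code will be broken and the subject withdrawn from the study". The section does not define the triggering event further, and does not separate stopping study medicine from leaving follow-up.
- **Follow-up and Outcomes.** FAS and SF-36 are collected at baseline and at weeks 4, 8 and 12; the post-baseline questionnaires are completed online. MYMOP is collected only at entry and at week 12. The number of subjects with FAS of 21 or below is compared at week 4.
- **Analysis.** The data will be "analyzed as if this were a full-scale trial in an intention to treat analysis by the study statistician". "Missing values will be handled by single imputation by last observation carried forward". No sentence removes a withdrawn subject from the analysis. Adverse events related in time to participation are documented, so the triggering event itself is recorded.

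**The concern.** Intention to treat relies on outcomes being sought from every randomised subject, whatever happens to their treatment. Here the protocol itself ends participation because of a post-randomisation event. Ordinary dropout cannot always be prevented, but this loss can: the outcomes are online self-reports that need neither blinded treatment nor a clinic visit.

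The loss may also be informative. Subjects with a severe event may differ in their later course from those without one, and the number of events may differ by arm. Carrying the last score forward then replaces what would have been observed with a value from before or around the event. At stake are the treatment comparison on FAS, SF-36 and MYMOP, and the FAS variability that the plan will use to size the full-scale trial.

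**Working it through.** **1. The rules read together.** The code-break rule withdraws the subject from the study. No section provides for questionnaires after that. The missing-data rule fills whatever is absent. So the subject remains in the randomised arm, with scores after the event imputed rather than observed. That questionnaires stop is the natural reading of withdrawal from the study; it is not stated outright.

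**2. Effect by outcome.**

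- *FAS and the eight SF-36 domains:* visits completed before the event keep their observed values; later visits repeat the last one.
- *MYMOP:* the only earlier value is the one at entry, so carrying it forward gives a change of exactly zero.
- *FAS of 21 or below at week 4:* entry requires FAS of 22 or above (Eligibility). A subject withdrawn before the week-4 questionnaire carries forward a baseline of at least 22 (taking baseline as the qualifying score) and counts as not returned to normal. A subject withdrawn after it already has an observed result. The rule cannot credit an arm with a false success here.

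**3. Size on FAS.** The plan gives no SD, event rate or effect size, so it has no figure to reproduce.

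Inputs from the documents: 66 subjects (Overview) and 1:1 allocation (Randomization and blinding), so 66/2 = 33 per arm.

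Assumed: a gap D of 5 to 15 FAS points between the true and carried-forward week-12 scores, and an SD of 7.

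Shift in an arm mean = k × D / 33, where k is the number of such subjects in that arm.

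| k in one arm, none in the other | D = 5 | D = 15 |
|---|---|---|
| 1 | 5/33 = 0.15 | 15/33 = 0.45 |
| 2 | 10/33 = 0.30 | 30/33 = 0.91 |

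Standard error of the arm difference = 7 × √(2/33) = 1.72.

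One subject therefore shifts the difference by 0.15/1.72 = 9% to 0.45/1.72 = 26% of a standard error. Two in the same arm with the largest gap give 0.91/1.72 = 53%. This is a simple week-12 comparison. The planned treatment-by-time test also uses the earlier, observed visits.

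**4. How often.** The chance of at least one code break among 66 is 1 − (1 − p)^66. For assumed event rates p of 1%, 2% and 5% it is 48%, 74% and 97%, with 66p = 0.7, 1.3 and 3.3 events expected.

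**5. FAS variability.** Suppose one subject is carried forward at the arm mean but truly lies D points away. The true sum of squares is larger by D² × 32/33. Divided by the 64 pooled degrees of freedom, this is D²/66: 25/66 = 0.38 or 225/66 = 3.41. Against a carried-forward variance of 7² = 49, the true variance is understated by 0.38/49.38 = 0.8% to 3.41/52.41 = 6.5%, and a sample size proportional to it by the same amount. A carried-forward score far from the mean could push the other way.

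**The case against.** The strongest reply has five parts.

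- *Nothing is contradicted.* A reader might infer that withdrawal from the study contradicts intention to treat. The documents do not support that: no sentence excludes withdrawn subjects, and the missing-data rule supplies values for them. This part stands in full.
- *The bias is presumed.* A reader might also infer that poor outcomes are being replaced by better ones, in favour of the arm with more events. The documents do not show that such an event worsens fatigue at week 12; an acute event may have resolved by then. This stands too: the direction is unknown, and the week-4 outcome cannot be flattered at all.
- *The rule will rarely matter.* It covers only events that are both severe and unexplained, in a 12-week pilot of 66 subjects where significance is not expected. This limits the severity. It does not remove the point, because the plan analyses the data as for a full-scale trial, and refining the design is one of its objectives.
- *The real fault is last observation carried forward.* That method affects every dropout, so it is a wider matter. But the avoidable loss would remain under any imputation method, and collecting the scores removes the need to impute them.
- *Later self-reports may be unblinded.* If the subject learns the allocation, expectation can colour the scores. This is a genuine cost, and can be handled by flagging.

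**Conclusion.** The point holds as a low-severity weakness. Following the plan as written appears to cause an avoidable and possibly informative loss of outcomes in subjects whose code is broken, and to fill the gap with earlier scores. It undermines the intention-to-treat analysis without contradicting it.

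If true scores after the event are worse than the carried-forward ones, the arm with more events is flattered on the continuous outcomes; if they are better, it is penalised. The documents do not settle which. The FAS shift is well under one standard error in every case tabulated. It would matter more only if events were frequent and fell mainly in one arm. These sizes rest on the assumed gap of 5 to 15 points and SD of 7, neither of which comes from the documents. The conclusion about follow-up rests on the plain meaning of withdrawal from the study; if the sponsor intends questionnaires to continue, the text needs to say so.

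**What to change.** In Randomization and blinding, separate leaving blinded treatment from leaving follow-up. State that after a code break the remaining scheduled online questionnaires continue unless the subject withdraws consent. In Analysis, state that the subject is analysed in the randomised arm with the scores actually observed. Flag scores given after the code break as possibly unblinded; a sensitivity analysis can set them aside.

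The cost is a sentence or two in each section and no new data collection beyond what is already scheduled. The downside is that the few later self-reports may carry expectation effects. Whether and how treatment continues after the event is for the sponsor and is not addressed here.

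### The scheduled safety question asks about side effects, which is narrower than the plan's own rule to document adverse events regardless of cause

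*Combined protocol and SAP*

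**What the plan says.** Two parts of the combined protocol and SAP deal with routine adverse event data.

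- **Methods, Follow-up (asking).** "Subjects will have follow-up visits by video with the homeopathic practitioners at 4, 8, and 12 weeks following the initial consultation". On safety, the section then says: "At each of these visits, the patients will be reevaluated, adverse side effects will be inquired about". At the same visits the prescription is renewed or changed.
- **Methods, closing paragraph of Analysis (recording).** The rule covers adverse events of any cause, not only those ascribed to the study medicine: an "event that occurs temporally related to participation in the study will be documented, whether or not it is considered to be related". The paragraph adds: "Serious and unexpected adverse experiences will be immediately reported by telephone to the Human Subjects Committee".

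Three other passages bear on the point. The Follow-up section says "The subjects will also complete online questionnaires at 4, 8 and 12 weeks after the initial visit to" evaluate outcomes, and no safety purpose is given for these forms. Randomization and blinding lets the code be broken early in one case: "An exception to this will be when a research subject suffers an unexplained severe event". The Background says that most homeopathic products "are without toxic side effects", because they are so dilute.

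**The concern.** A recording rule can act only on events that come to light. The one scheduled step described for bringing them to light is a question about side effects. A subject who has had an infection, an injury, a new diagnosis or a change in ordinary medication may answer no, and answer truthfully, because they do not think the study medicine caused it. Under the recording rule such an event belongs in the data. Under the visit wording it may never be mentioned.

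Two things are at stake. A low count could partly reflect how the question was put, yet be read as reassurance. And testing and refining the treatment protocol for a larger trial is one of the pilot's Technical Objectives, so a narrow question left unchanged here could be carried into that trial.

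**Working it through.** The plan states no safety figure to reproduce, so the check is a comparison of texts.

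**1. Scope of each text**

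| | Follow-up section | Closing paragraph of Analysis |
|---|---|---|
| Step | Asking | Recording |
| Object | Side effects | Any adverse event linked in time to participation |
| Causality needed? | Yes, on the ordinary meaning of the term | No, expressly excluded |
| Timing | Weeks 4, 8 and 12 | Throughout participation |

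One text governs asking and the other recording, so both can be obeyed at once and they do not strictly contradict each other. But the scheduled input is narrower than the output it is meant to supply.

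**2. Other scheduled routes.** The online questionnaires serve outcome evaluation. The instruments named are the FAS and SF-36 at baseline and weeks 4, 8 and 12, and MYMOP at entry and week 12 only. No adverse event item is described, although the forms themselves are not in the documents. Adverse events appear neither in the Outcomes list nor in the Analysis bullets, so no alternative method of collection is set out there. The re-evaluation at each visit is a route by which events can surface, but nothing says what it must cover for safety.

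**3. Reach of the wording.** The Overview reads "In this double-blind pilot study, 66 patients who have tested positive for COVID-19 and" goes on to describe the two arms. With three follow-up visits each, the wording governs at most 66 × 3 = 198 scheduled inquiries. That is the number of times the question is put, not a number of lost events.

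**4. Size of any loss.** Let *a* be the share of events that someone attributes to the medicine, and *c* the share of the remaining events that surface anyway, through re-evaluation or because the subject volunteers them. If every attributed event is recorded, then

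share recorded = *a* + (1 − *a*) × *c*

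share lost = (1 − *a*) × (1 − *c*)

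If *c* = 1, nothing is lost. If *c* = 0, every unattributed event is lost. The documents give neither *a* nor *c*, nor the underlying event rate, so the loss cannot be narrowed within these limits.

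**The case against.** The strongest reply is that this is loose drafting and no more. Side effects may simply be shorthand for adverse events, and the script put to subjects is not given. Licensed practitioners re-evaluate every subject at every visit, so new illness can surface whatever the prompt says, and once known it must be documented regardless of cause. Serious and unexpected events have their own immediate reporting rule. Estimating safety is not among the six Technical Objectives. Only the pharmacist knows the allocation, so blinded practitioners put the same question in both arms, and any under-ascertainment should be largely similar between them.

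Most of this stands, and it limits what can be claimed. A reader might infer any of the following, but the documents do not support them:

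- **That the safety data will be incomplete or filtered by causality.** The recording rule forbids such a filter, and re-evaluation gives events another way in. Under-ascertainment is a risk, not a demonstrated result.
- **That a subject who misses a visit is never asked.** Someone who misses week 4 or week 8 is due to be asked at the next visit. Only after a missed week 12 visit is no later inquiry described.
- **That the Background sentence on toxicity will suppress attribution.** It is a general remark about dilution. Nothing makes it an attribution rule or says that subjects are told it.

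What the reply does not remove is the gap in wording. Similar under-ascertainment in both arms would still lower both counts. The re-evaluation is described alongside prescribing, with no stated instruction to look for unrelated events. And if the sponsor already means adverse events, saying so costs nothing.

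**Conclusion.** The point holds in a limited form. The only scheduled safety inquiry described is worded more narrowly than the recording rule it serves, so events that nobody ascribes to the medicine may be under-ascertained. This rests on the ordinary meaning of side effect and on the absence of any other described inquiry. A neutral script or a safety item on forms not included in the documents would largely answer it. No figure for lost events is justified. Severity is minor: a cheap improvement in how events are elicited, with no consequence shown for the efficacy analysis.

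**What to change.** 1. In the Follow-up section, replace the clause on side effects with an open question put to all subjects at each visit, for example: *Since our last contact, have you had any new or worsened health problem, any medical visit, or any change of medication?*
2. Add the same item to the online questionnaires already sent at weeks 4, 8 and 12. This gives a second route that does not depend on the prescribing conversation, and it covers the last interval for someone who returns the week 12 form but misses the visit.
3. Record judged causality afterwards, in its own field, while the subject's allocation is still concealed. The code may be opened once each subject's treatment is complete, so the entry should be made before then.

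A further rule, that every symptom prompting a change of medicine counts as an adverse event, is not recommended here. In a fluctuating, multi-symptom syndrome it could log ordinary variation as harm.

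The cost is one protocol sentence, one item on existing forms and one data field. The downside is a longer list of minor events to log. Both changes would go to the Human Subjects Committee, as the plan requires for any modification.

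### MYMOP has no assessment between entry and week 12, so carry-forward scores anyone missing week 12 as unchanged, and the MYMOP time course cannot be described

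*Combined protocol and SAP*

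**What the plan says.** The MYMOP schedule is stated three times, and the three statements agree.

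- Methods, Overview: "The MYMOP score of specific symptoms will be administered at entry to the study and at the end of 12 weeks".
- Outcomes, under "Secondary outcome measurements": "each patient chooses the two most bothersome symptoms to record and follow (at study entry and at the end of 12 weeks".
- Analysis: "The Measure Yourself Medical Outcomes Profile (MYMOP) collected at baseline and at week 12 will be analyzed by independent sample t-test", with a rank-sum test if the data are not normal.

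The primary questionnaires follow a fuller schedule. Outcomes lists "Fatigue Assessment Score (FAS) at baseline, week 4, week 8 and week 12" and gives SF-36 the same four time points. The Follow-up paragraph confirms that the contacts exist: subjects "complete online questionnaires at 4, 8 and 12 weeks after the initial visit".

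The Analysis section calls for intention to treat, with missing values filled by single imputation using the last observation. It makes no exception for MYMOP. Technical Objectives includes "3) evaluate the instruments for assessing treatment outcomes", without a criterion or a required number of assessments. No reason is given for leaving MYMOP out at weeks 4 and 8.

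**The concern.** A carry-forward rule needs something to carry. For FAS and SF-36, a subject who answers at week 4 or 8 and then drops out contributes an on-treatment score. For MYMOP no such score can exist, so the rule becomes baseline carried forward, and each missing week-12 value enters the comparison as exactly zero change.

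Two things are at stake. The first is the MYMOP effect estimate and its SD: zeros dilute a real difference, and they can produce an apparent one if the arms lose different numbers of subjects. The second is what the pilot can learn about the instrument. MYMOP is the only listed outcome built on each patient's own chosen symptoms, in a trial of individualized prescribing where prescriptions may be revised at weeks 4 and 8. The plan cannot show how those symptoms stood at either visit, nor set the MYMOP course beside those of FAS and SF-36.

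**Working it through.** The documents give no power, effect size, SD, dropout rate or precision target for MYMOP, so there is no figure of the plan's own to reproduce.

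**Inputs from the documents:** 66 subjects (Overview); 1:1 allocation, so 66 / 2 = 33 per arm (Randomization and blinding); two-sided 0.05 and last observation carried forward (Analysis); MYMOP at entry and week 12 only.

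**Assumed inputs:** week-12 missingness d of 10%, 20% or 30%; true mean improvement μ of 1.0 SD on active treatment and 0.5 SD on placebo. These only illustrate the mechanism.

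**Step 1. Equal missingness, unrelated to outcome.** Each arm's expected change is (1 − d) × μ + d × 0 = (1 − d)μ, so the arm difference is (1 − d) times the true one. The Analysis section does not say whether the t-test uses change or week-12 scores. Because the arms are randomized, the expected shrinkage is the same either way.

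**Step 2. Effect on SD and power.** With baseline carried forward, an arm's variance of change is (1 − d)(1 + μ²) − [(1 − d)μ]². At d = 20%:
- active: 0.8 × 2 − 0.8² = 0.96
- placebo: 0.8 × 1.25 − 0.4² = 0.84
- pooled SD: √[(0.96 + 0.84)/2] = 0.949

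| Missing d | Subjects (66d) | Difference, baseline carried forward (SD units) | Pooled SD | Power, baseline carried forward | Power, completers only |
|---|---|---|---|---|---|
| 0% | 0 | 0.50 | 1.000 | 53% | 53% |
| 10% | 6.6, about 7 | 0.45 | 0.978 | 46% | 48% |
| 20% | 13.2, about 13 | 0.40 | 0.949 | 40% | 44% |
| 30% | 19.8, about 20 | 0.35 | 0.912 | 34% | 40% |

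The rule shrinks the SD as well as the difference.

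**Step 3. Unequal missingness.** Suppose both arms truly improve by 1.0 unit, with 10% missing in one and 25% in the other. The plan would report 0.90 × 1.0 = 0.90 against 0.75 × 1.0 = 0.75, an apparent difference of 0.15 where the true one is zero.

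**Step 4. What interim scores could restore.** Take a favourable case: every subject missing week 12 has a week-8 score, and 75% of the effect is present by then. Carrying week 8 forward gives (1 − d) × 0.50 + d × 0.375, that is 0.49, 0.48 and 0.46 SD at 10%, 20% and 30% missing, against 0.45, 0.40 and 0.35 under the plan. The gain is smaller if fewer of these subjects answered at week 4 or 8.

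**Step 5. What two time points still give for objective 3.** With m completers and m − 2 degrees of freedom, the 95% limits for the SD of change are √(df/χ²) at the 97.5% and 2.5% points, expressed as multiples of the estimate:
- 66 completers: 0.85–1.21
- 59 completers: 0.85–1.22
- 53 completers: 0.84–1.24
- 46 completers: 0.83–1.26

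The week-12 SD is estimated almost as well with 53 completers as with all 66. What is absent is any observation between entry and week 12.

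**The case against.** The strongest reply is that measuring a secondary outcome before and after treatment is a legitimate pilot choice, applied consistently, and that the quantified harm comes from the imputation rule rather than the schedule. Much of this stands.

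- **Objective 3.** A reader might infer that it cannot be met for MYMOP. The documents do not support that. The objective sets no criterion, and entry and week-12 data give completion, change, its SD, the arm difference and a comparison with FAS and SF-36 change at week 12. How strongly MYMOP responds can be compared; how early cannot.
- **Missing-data method.** A reader might also infer that no other method would help. That fails too. If missingness is equal and unrelated to outcome, an analysis of completers shows no shrinkage in expectation, and interim FAS and SF-36 scores could inform an imputation. No method, however, supplies an observed interim MYMOP score.
- **Importance.** FAS and SF-36 are primary, and the Analysis section sizes the full trial from FAS variability. Nothing makes MYMOP a candidate primary outcome.
- **Size.** Under intention to treat with online questionnaires, stopping treatment need not mean a missing score. Three scores per subject instead of one would not triple the information, because repeats within a subject are correlated.
- **Burden.** Fewer questions may suit patients with fatigue and cognitive difficulty, although the plan does not give this as its reason. Eligibility already requires willingness to complete regular questionnaires.

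The reply does not remove the interaction between schedule and rule. As written, the plan applies carry-forward to an outcome that has nothing but baseline to carry.

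**Conclusion.** The point holds as a worthwhile, low-cost design improvement. It is neither a contradiction nor a flaw that defeats an objective. Under the plan as written, anyone missing week 12 is scored as unchanged on MYMOP. At an assumed 10–20% missing (about 7 to 13 of 66), equal between arms and unrelated to outcome, the expected arm difference is 0.90 to 0.80 of the true one. If missingness differs by arm, the comparison can be biased and a spurious difference can appear.

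The shrinkage factor depends only on d under those conditions. The power and SD figures depend also on the assumed effects, and they matter less here because the Analysis section itself expects few significant results. Replacing carry-forward would remove much of the shrinkage without changing the schedule. The lasting loss is the MYMOP time course and any on-treatment score for later dropouts, which cannot be recovered once the weeks have passed.

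**What to change.** In Overview, Outcomes and Analysis, add MYMOP to the existing week-4 and week-8 online questionnaires, scoring the same two symptoms nominated at entry. In Analysis:

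- keep the week-12 between-arm comparison as the main MYMOP result;
- use the interim scores for subjects missing week 12 in place of carrying baseline forward, preferably in a likelihood-based repeated-measures model with the week-12 treatment contrast, rather than by last observation carried forward;
- describe the MYMOP time course beside FAS and SF-36 under objective 3, and report MYMOP completion by arm and week.

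The cost is a few more items at two sessions that already take place, a small amendment approved by the Human Subjects Committee, and slightly more respondent burden. The change does nothing for subjects lost before week 4, and its benefit depends on how many of those missing week 12 answered at week 4 or 8.

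If the sponsor prefers to keep two time points, the minimum change is to exempt MYMOP from carry-forward, name the method that replaces it, and report completion by arm. That addresses the zero-change scoring but leaves the time course unobserved.
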